2.4.6.2 Additional safety endpoints not defined in the protocol

2.4.6.2.1 Freedom from device related serious adverse events prior to discharge.

Derivation is described in section 2.1.4.1.1. Results will be summarized using frequency tables for the SAS and by subpopulation (prospective/retrospective) and by procedure type. Exact 95% confidence limits will be presented.

2.4.6.2.2 Freedom from device related adverse events prior to discharge.

Derivation is described in section 2.1.4.1.2. Results will be summarized using frequency tables for the SAS and by subpopulation (prospective/retrospective) and by procedure type. Exact 95% confidence limits will be presented.

2.4.6.2.3 Re-admission within 30 days

As per section 2.1.4.1.3, each patient in the SAS will be assigned to 'Yes' or 'No' for re-admission and the time to re-admission derived.

Patients classified as re-admission = "Yes" will be classified as events, and other patients will be censored. A Kaplan Meier plot will be produced for time to re-admission, overall, by subpopulation (prospective/retrospective) and by procedure type (flap, replantation, lymphatic). From the Product Limit Estimator (PL estimator), an estimate of re-admission rate within 30 days will be obtained.

2.4.6.2.4 Re-operation within 30 days

As per section 2.1.4.1.4, each patient in the SAS will be assigned to 'Yes' or 'No' for re-operation and the time to re-operation derived.

Patients classified as re-operation = "Yes" will be classified as events, and other patients will be censored. A Kaplan Meier plot will be produced for time to re-operation, overall, by subpopulation (prospective/retrospective) and by procedure type (flap, replantation, lymphatic). From the Product Limit Estimator (PL estimator), an estimate of re-operation rate within 30 days will be obtained.

Re-operation rate will be evaluated for consistency with the re-operation rates reported in the UK National Flap Registry (UKNFR), where the overall re-operation rate was 10.7% (95% confidence limits 9.8%, 11.7%). The re-operation rate within 30 days for the Symani system will be presented with 95% confidence limits.

Sponsor: MMI Product: Symani system for microsurgical anastomosis Study: PRIMO	
Statistical Analysis Plan Final 22 November 2024	

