2. STATISTICAL AND ANALYTICAL PROCEDURE

The study has a hierarchical structure as follows:

- There are three types of surgery: free flaps, replantations, and lymphatic. A patient may have more than one type of surgery (e.g flap and replantation).
- Within a type of surgery, e.g. free flaps, a patient may have more than one procedure during an operation.
- Within each procedure, anastomoses are performed. More than one anastomosis may be performed within a procedure.

For the purpose of this SAP, endpoints may be defined at any of these levels, i.e. patient, surgery type, procedure within a surgery type, anastomosis within procedure. This hierarchy is described in Figure 1. The unit of analysis for each endpoint will be clearly defined in this SAP.

Sponsor: MMI Product: Symani system for microsurgical anastomosis Study: PRIMO	
Statistical Analysis Plan Final 22 November 2024	

Figure 1 hierarchy of dependence in the endpoint data.

Level			
Surgery type within patient	Free flap	Replantation	Lymphatic
Procedure within surgery type	FF1, FF2, FF3 etc	R1, R2, R3 etc	LVA1, LVA2, LVA3 etc
Anastomosis within procedure	FF1A1, FF1A2, FF2A1, FF2A2, FF3A1, FF3A2, etc	R1A1, R1A2, R2A1, R2A2, R3A1, R3A2, etc	LVA1A1, LVA1A2, LVA2A1, LVA2A2, LVA3A1, LVA3A2, etc

In addition to this hierarchical structure regarding the initial attempt, for a particular anastomosis, there may be the need for an intraoperative redo within the same operation (a secondary endpoint), or the need for a re-operation on a subsequent date (a secondary endpoint). This patient flow is described in Figure 2.

[figure not shown]

Sponsor: MMI Product: Symani system for microsurgical anastomosis Study: PRIMO	
Statistical Analysis Plan Final 22 November 2024	

Figure 2. Patient flow through study procedures

Note. Procedure = flap or replantation or lymphatic. [1] There may be > 1 procedure done. A second procedure may be the same type as procedure 1 (e.g 2 flaps procedures) or may be different. The figure suggests 2 procedures (due to space limitations) but there may be > 2 procedures.

Sponsor: MMI Product: Symani system for microsurgical anastomosis Study: PRIMO	
Statistical Analysis Plan Final 22 November 2024	

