2.2.3 Safety populations

2.2.3.1 Safety Analysis Set (SAS)

The SAS will include all patients in the AES that had at least one robotic suture placed or attempted. Note that this definition will include all patients in the FAS as well as any other patients outside of this set (but in the All Enrolled Set) where robotic anastomosis is attempted but no robotic sutures placed. To classify as 'robotic anastomosis attempted' there will be a robotic time recorded on the CRF for at least one anastomosis.

As for the SAS, two sub-populations will be defined based on the SAS.

- The prospective patient sub-population
- The retrospective patient sub-population.

All summaries and analyses will be presented using all data combined and by sub-population.

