2.4.4.3.1 Free-flap survival rate at 30 days

As per section 2.1.3.5.1 each flap for each patient in the FAS will be assigned to 'Yes' or 'No' for free flap survival at 30 days. This represents a binary outcome. The analysis of this variable is at the procedure (flap) level. Summary and analysis will be as described above for flap loss/failure (Model 4).

Sponsor: MMI Product: Symani system for microsurgical anastomosis Study: PRIMO	
Statistical Analysis Plan Final 22 November 2024	

In addition, the effectiveness of the Symani System will be evaluated for consistency with the free flap success rates reported in the UK National Flap Registry [1], where the overall free flap survival rate was 96.0% (95% confidence limits, 95.4%, 96.6%)."

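### SAP 2.4.6.2.4 does not restrict the re-operation rate set against the flap registry's 10.7% to flap patients; read literally, it is the rate for all surgery types, so the check depends on case mix

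*SAP*

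**What the plan says.** Section 2.4.6.2.4 of the SAP defines the endpoint on the whole safety set: "each patient in the SAS will be assigned to 'Yes' or 'No' for re-operation". Section 2.2.3.1 sets no limit by surgery type: "The SAS will include all patients in the AES that had at least one robotic suture placed or attempted". Section 2 lists what that covers: "There are three types of surgery: free flaps, replantations, and lymphatic".

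Section 2.4.6.2.4 plans Kaplan-Meier plots overall and also "by subpopulation (prospective/retrospective) and by procedure type (flap, replantation, lymphatic"), and a product-limit estimate of the 30-day rate. The comparison follows: "Re-operation rate will be evaluated for consistency with the re-operation rates reported in the UK National Flap Registry (UKNFR"). The benchmark it gives is 10.7%, with limits of 9.8% and 11.7%. The section closes with a single rate: "The re-operation rate within 30 days for the Symani system will be presented with 95% confidence limits". No sentence says which of the planned estimates is set against the registry, and none says what would count as consistent.

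The same registry is used once more, in section 2.4.4.3.1, where the device is to be "evaluated for consistency with the free flap success rates reported in the UK National Flap Registry". There the analysed variable is survival of each free flap.

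**The concern.** A benchmark from a flap registry is informative about flap patients. In the survival comparison the SAP sets flaps against flaps. In the re-operation comparison the only population named is the full safety set, and the rate reported with limits is described as that of the system as a whole. Followed literally, a mixed surgical population is set against a flap population.

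This comparison is an external safety check on the device. If its result moves with the proportion of lymphatic or replantation patients who happen to be enrolled, neither agreement nor disagreement with 10.7% says much about flap surgery with the device. Leaving the cohort open also allows it to be chosen after the estimates have been seen. The problem does not depend on data capture: even if every re-operation were recorded, the two populations would still differ.

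**Working it through.** **Inputs**
- Registry re-operation rate 10.7% (9.8% to 11.7%): SAP 2.4.6.2.4.
- Registry free flap survival 96.0% (95.4% to 96.6%): SAP 2.4.4.3.1.
- Planned minimum of 402 patients: SAP 1.7, used here as the illustrative size of the safety set.
- Flap share *w*, flap rate *p* and non-flap rate *q*: not in the documents. All values below are assumptions. Simple proportions stand in for the Kaplan-Meier estimates, and limits are exact binomial.

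**1. The plan's own figure.** The SAP gives no numerator or denominator for the 10.7%, so it cannot be recomputed. It is coherent with the other registry figure. A half-width of 0.6 points around 96.0% implies n = 0.96 × 0.04 × (1.96/0.006)² ≈ 4,098, and the exact interval for 10.7% with about 4,000 to 4,100 observations is 9.8% to 11.7%. The benchmark is taken as given.

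**2. Flap rate behind a pooled 10.7%.** The pooled rate is *wp* + (1 − *w*)*q*. Setting it to 0.107 gives *p* = [0.107 − (1 − *w*)*q*] / *w*.

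| Flap share | *q* = 0% | *q* = 2% | *q* = 5% |
|---|---|---|---|
| 50% | 21.4% | 19.4% | 16.4% |
| 60% | 17.8% | 16.5% | 14.5% |
| 80% | 13.4% | 12.9% | 12.1% |
| 90% | 11.9% | 11.7% | 11.3% |

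For example, at 60% and 5%: (0.107 − 0.4 × 0.05)/0.6 = 0.145.

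**3. With sampling error, 402 patients.**
- 60% flap, no events elsewhere: pooled 43/402 = 10.7% (7.8% to 14.1%), which looks consistent. Flap only: 43/241 = 17.8% (13.2% to 23.3%), wholly above the registry's upper limit of 11.7%.
- 80% flap, 2% elsewhere: pooled 50/402 = 12.4% (9.4% to 16.1%), which includes 10.7%. Flap only: 48/322 = 14.9% (11.2% to 19.3%), which does not.

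**4. The opposite error.** If the flap rate equals the registry's 10.7%, then at a 60% flap share the pooled rate is 0.6 × 0.107 + 0.4*q*: 6.4% for *q* = 0 and 8.4% for *q* = 5%. That is an apparent advantage produced by case mix alone.

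**5. When the bias vanishes or reverses.** With *q* = 10.7%, a pooled 10.7% means a flap rate of 10.7%. With a 25% non-flap share and *q* = 15%, it means (0.107 − 0.25 × 0.15)/0.75 = 9.3%. With 60% flap at 43/241 and 32/161 elsewhere (about 20%), the pooled rate is 75/402 = 18.7% (15.0% to 22.8%), and nothing is masked.

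**6. Who enters the pooled rate.** The derivation in section 2.1.5.1.4 draws on the free flap operation form and the recipient-site forms and lists no lymphatic operation form. It censors patients with no recorded re-operation at their last follow-up date. On that reading, lymphatic patients enter largely as non-events, near the *q* = 0% column. Section 2.5.2, however, excludes patients whose outcome cannot be determined. If it were applied to lymphatic patients, there would be less dilution. The SAP does not settle which applies.

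**The case against.** The strongest reply is that the SAP never says the pooled rate is the one compared. The flap curve is planned in the same section, and section 2.4.1 identifies the three surgery cohorts for reporting, so a raised flap rate would appear beside the pooled one. This stands. A reader might infer that the SAP expressly compares the whole set, or that a raised flap rate would be hidden from view; the text supports neither. But the SAP does not tie the flap estimate to the 10.7%, nor does it clearly promise confidence limits for it.

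A second reply is that the direction of bias is assumed. This also stands. The documents contain no case mix and no lymphatic or replantation re-operation rates, and section 2.1.2 says that a replantation may itself be of the free flap kind, so replantation patients cannot be treated as plainly unlike flap patients. A reader might infer that pooling necessarily pulls the rate down towards the registry. That would need lower non-flap rates, which the documents do not show.

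Third, the stakes are limited. The endpoint is an addition not defined in the protocol, and the comparison is descriptive, with no test, margin or decision rule. That bears on priority. It does not make an unlike comparison interpretable.

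**Conclusion.** The point holds in this form: the rate set against the flap registry is not restricted to flap patients, and its literal reading is the rate for all procedures in the Safety Analysis Set. The result of the check therefore depends on enrolled case mix, whichever way the bias runs.

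The size is illustrative only. At an assumed 60% flap share and non-flap rates of 0% to 5%, a pooled 10.7% would go with a flap rate of 14.5% to 17.8%. At a 90% flap share the range is only 11.3% to 11.9%. If the non-flap rate exceeds the flap rate, the pooled figure overstates the flap rate and could raise a false alarm. The point does not touch the primary endpoint. It is worth correcting because a statement of consistency on safety could mislead and because the right estimate is already planned.

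**What to change.** In section 2.4.6.2.4, state that only the Kaplan-Meier 30-day estimate for patients with a free flap procedure, with its 95% confidence limits, is set against the registry's 10.7%, in line with the flap-level comparison in section 2.4.4.3.1. State that the overall, replantation and lymphatic rates are reported descriptively without this benchmark. The same edit should say how patients with both a flap and a lymphatic procedure are counted, and give the unit and time window of the registry figure, which the SAP omits; without these, some mismatch may remain even within flap patients.

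The change takes a few sentences and no new data, since the flap stratum is already planned. The cost is precision. At a rate of 10.7%, the approximate 95% half-width is 1.96 × √(0.107 × 0.893/402) = 3.0 points for 402 patients and 1.96 × √(0.107 × 0.893/241) = 3.9 points for 241 flap patients (the assumed 60% share).

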2.4.6.2.5 Death within 30 days

As per section 2.1.4.1.5, survival time for each patient will be determined. Patients noted to be dead will be classified as events, and other patients will be censored. A Kaplan Meier plot will be produced for survival time, overall, by subpopulation (prospective/retrospective) and by procedure type (flap, replantation, lymphatic). From the Product Limit Estimator (PL estimator), an estimate of death within 30 days will be obtained.

2.4.6.2.6 Length of hospital stay

As per section 2.1.5.1.6 the length of hospital stay (in days) for each patient in the SAS will be derived. Results will be summarized using descriptive statistics for the SAS overall, by subpopulation (prospective/retrospective) and by procedure type (flap, replantation, lymphatic).

2.5 Statistical/ Analytical Issues

2.5.1 Adjustments for covariates

Surgery type (flap, replantation, lymphatic) and subpopulation (prospective/retrospective) are included as fixed factors where applicable in the primary and secondary efficacy modelling. Results by these factors are included in tables and forest plots produced for the study.

Surgeon is included as a random effects term in each of the models.

Procedure number/anastomosis number (within patient) are included in models where relevant to acknowledge dependence in the data.

2.5.2 Handling of Dropouts or missing data

For all outcomes, if there is insufficient information available to determine the outcome (including for the continuous measure of length of hospital stay), the patient will be excluded from the analysis in question.

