1.7 Determination of sample size

The planned minimum sample size is 402 patients. The primary endpoint for the study is technical performance, assessed as a binary outcome procedural success Yes/No. Procedural success will be assessed at the anastomosis level; each patient may have > 1 anastomosis. Based on data published in the medical literature (see RASM Literature Review Report [5]), the traditional failure and complication rate for vascular anastomoses is 15%, implying a success rate of 85%. The study will have 85% power to conclude that a success rate using Symani of 89% (or higher) is better than the literature value if a minimum of 402 anastomoses operations are performed. The percentage success will be estimated and exact 95% confidence limits calculated. If the lower 95% confidence limit exceeds 85% then the conclusion can be reached that Symani is superior to manual surgical methods. As each patient may have more than one anastomosis operation, the number of anastomoses will be ≥ 402 from 402 patients, providing increased power. As the number of anastomoses/patient is unknown at the time of study design, the conservative approach of recruiting 402 patients has been followed.

The number of patients missing a response for the primary endpoint will be monitored and additional patients may be recruited if deemed necessary.

There will be no predetermined limit to the number of sites that can participate in the study. Patients enrolled under the retrospective data collection protocol addendum will contribute to the planned sample size for the entire study (prospective plus retrospective).

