2.1.3.1 Primary effectiveness endpoint – Procedure Robotic Success

Form R or Anastomosis Data Form will be completed for each anastomosis. If the answer to the question 'How did you intend to perform this anastomosis' is 'Robotic' then the anastomosis is included for this endpoint.

The endpoint will be derived for each anastomosis using the question "Did you experience any system technical issues resulting in unplanned return to conventional suturing".

If the response is 'No' and the number of robotic sutures is > 0 or the number of robotic redo sutures is > 0, the anastomosis will be classified as 'intra-operative change from robotic to manual' = 'no'.

If the response is 'yes' anastomosis will be classified as intra-operative change from robotic to manual = 'yes'.

If there is no response to the question the anastomosis classification will be missing.

If the planned approach was manual the result will be N/A

The unit of analysis for this endpoint is the anastomosis.

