If there is a device related SAE but the onset date is after the date of discharge, and the patient has no other event to classify them as having a device related SAE prior to discharge, then they will be classified as free from device related SAE prior to discharge = yes. Otherwise, if there is a SAE that is define as device relates SAE = Yes, then the patient will be classified as free from device related SAE prior to discharge = No.

If it is not possible to classify the event, the patient's classification will be missing. A supporting analysis will use freedom for device related SAE prior to discharge = No for all unclassified patients.

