2.5.6 Statistical technical issues

The models noted in the efficacy analyses propose a default covariance structure of type=VC, which is a simple diagonal matrix with equal variances across all levels of the surgeon ID variable. This will be examined to determine if the structure is appropriate, or whether an alternative structure is more appropriate. The use of the GROUP= option in the random statement may also be investigated if type=VC does not adequately explain the variance observed across surgeons (that is, including GROUP=surgeon in the random statement). This will be done as part of normal model checking procedures and described as part of the reported statistical analysis results.

The retrospective data collection may have a reasonable amount of missing data. All data available will be used as much as possible and the derivation of the effectiveness endpoints defines how to obtain a result if possible. All data summaries will clearly indicate the amount of missing data.

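### The primary endpoint is analysed on complete cases only, and no planned analysis shows whether the superiority conclusion against 85% depends on the missing outcomes

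*SAP*

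**What the plan says.** The primary endpoint, procedure robotic success, is derived for each anastomosis intended to be robotic, from a question on whether technical issues forced an unplanned return to conventional suturing. SAP 2.1.3.1 states: "If there is no response to the question the anastomosis classification will be missing". SAP 2.2.2.1 limits each effectiveness analysis to non-missing data. SAP 2.5.2 applies a general rule to all outcomes: if the outcome cannot be determined, "the patient will be excluded from the analysis in question". That rule speaks of the patient, whereas the unit for this endpoint is the anastomosis.

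SAP 2.4.4.1 specifies frequency tables, a forest plot and a mixed model for the primary endpoint. It contains no analysis that varies the handling of missing outcomes.

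SAP 1.7 attaches a decision to the result. "The percentage success will be estimated and exact 95% confidence limits calculated", and a lower limit above 85% is to be read as superiority over manual surgery.

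Three other provisions bear on the point:
- SAP 2.5.6 expects gaps: "The retrospective data collection may have a reasonable amount of missing data". Retrospective patients count towards the target sample size (SAP 1.5 and 1.7).
- SAP 1.7 says that missing primary responses will be monitored and that more patients may be recruited. SAP 2.4.1 and 2.5.6 require missing counts to be displayed.
- For a safety endpoint, SAP 2.1.5.1.1 already plans an unfavourable-value analysis: "A supporting analysis will use freedom for device related SAE prior to discharge = No for all unclassified patients".

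**The concern.** The comparison is with a fixed external figure and there is no control arm. If anastomoses with no answer failed more often than those with one, the observed success rate would be too high, and no second group would carry a similar error to offset it. The claim therefore rests on an untested assumption that the missing cases resemble the observed ones.

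At stake is the only formal decision rule in the SAP. Near the 85% boundary, a few unanswered forms can separate a claim from no claim. Unless the check is specified in advance, whether and how to make it will be decided after the pattern of missing data is known.

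**Working it through.** **Inputs.** From SAP 1.7: N = 402 ("if a minimum of 402 anastomoses operations are performed"), benchmark 85%, assumed true rate 89%, stated power 85%, exact 95% limits. These are read as two-sided, so 2.5% lies in the lower tail. From SAP 2.1.3.1: the unit is the anastomosis. The missing rates of 1%, 2%, 5% and 10% are assumptions. Anastomoses are treated as independent.

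**Formula.** For x successes in n, the exact (Clopper-Pearson) lower limit is the 0.025 quantile of Beta(x, n − x + 1). The rule is met if this exceeds 0.85.

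**The plan's own figure.** At n = 402, 356 successes (88.6%) give a lower limit of 85.03% and 355 give 84.76%, so the rule needs 356. Exact power at a true 89% is P(X ≥ 356) = 64.9%, not the stated 85%. That is a separate matter, and nothing below depends on it.

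**Step 1: observed success needed.** With m missing, the complete-case analysis uses n = 402 − m. Counting missing as failure restores the denominator to 402, so 356 successes must come from the 402 − m observed.

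| Missing | Observed n | Complete-case minimum | Missing = failure minimum |
|---|---|---|---|
| 4 (1%) | 398 | 353 (88.7%) | 356/398 = 89.4% |
| 8 (2%) | 394 | 349 (88.6%) | 356/394 = 90.4% |
| 20 (5%) | 382 | 339 (88.7%) | 356/382 = 93.2% |
| 40 (10%) | 362 | 322 (89.0%) | 356/362 = 98.3% |

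**Step 2: the bound with 20 missing.**
- 340/382 (89.0%): lower limit 85.4%, rule met. As 340/402 (84.6%): lower limit 80.7%, not met.
- 344/382 (90.1%): lower limit 86.6%, rule met. As 344/402 (85.6%): lower limit 81.8%, not met.

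**Step 3: tipping points with 20 missing.** If k of the 20 are failures, total successes are x + 20 − k, and the rule needs x + 20 − k ≥ 356, so k ≤ x − 336.

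| Observed | Largest k that keeps the claim | Claim lost at |
|---|---|---|
| 340/382 (89.0%) | 4 | 5 of 20 (25%) |
| 344/382 (90.1%) | 8 | 9 of 20 (45%) |
| 348/382 (91.1%) | 12 | 13 of 20 (65%) |
| 356/382 (93.2%) | 20 | never |

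**Step 4: more anastomoses.** SAP 1.7 expects at least 402 from 402 patients. At 89% observed and 5% missing, the lower limits (complete case against missing = failure) are 86.5% and 81.8% for N = 800, and 86.9% and 82.2% for N = 1000. A larger N does not remove the reversal at the bound.

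**The case against.** The strongest reply has four parts.

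- **The plan does not ignore missing data.** It monitors missing primary responses, allows further recruitment, and tabulates missing units overall and by prospective/retrospective. A reader could work out the missing-as-failure bound from those tables. This stands, and it would be wrong to infer that the information will be unavailable. But recruitment replaces numbers rather than the missing results, and displaying counts does not commit anyone to test or qualify the claim.
- **No missing rate is given.** The protocol synopsis has a 5% dropout allowance, but this outcome is recorded during surgery, so later dropout need not make it missing. The remark about retrospective gaps in SAP 2.5.6 is general and does not name this question. This stands too: a reader might infer that 5% missing is expected here, and the documents do not say so.
- **Missing = failure is an extreme.** At 344/382 the claim survives 8 of 20 missing cases failing (40%), about four times the observed failure rate of 38/382 (9.9%). This is why the bound needs a tipping point beside it.
- **The direction of any bias is unknown.** A reader might infer that blanks conceal failures. The documents do not support that; a blank could equally mean that nothing went wrong.

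The safety analysis in SAP 2.1.5.1.1 also creates no contradiction with the primary endpoint. It shows only that the sponsor uses this kind of check elsewhere.

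**Conclusion.** The gap is real and worth closing before analysis: complete-case handling, a claim against a fixed 85%, and no prespecified test of whether that claim depends on the missing outcomes. Its size depends on the observed rate and on how much is missing. At the planned 89% with 5% assumed missing, 5 failures among the 20 missing are enough to lose the claim. At 93.2% observed or above, 5% missing cannot reverse it. At 1% missing, the worst case raises the requirement only to 89.4%.

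It would go too far to say that missing data will decide the result, or that the claim is biased upwards. The documents establish neither.

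The figures assume 402 independent anastomoses, the pooled two-sided exact limit of SAP 1.7, and exclusion by anastomosis. SAP 2.4.4 itself says that limits assuming independence are biased. If 2.5.2 is applied literally, by patient, one blank could remove all of a patient's anastomoses and these counts would not apply.

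**What to change.** 1. In SAP 2.4.4.1 and 2.5.2, state that exclusion for the primary endpoint is by anastomosis, not by patient.
2. In the same sections, add a supporting analysis of all robotic-intended anastomoses in the FAS with missing outcomes counted as failures, labelled as the bound.
3. Add a tipping-point result: the smallest number and share of missing outcomes that must be failures for the lower limit to fall to 85% or below.
4. Present both overall and by prospective/retrospective.
5. In SAP 1.7, state that if the bound changes the conclusion, the superiority statement will be qualified with the tipping point.

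The cost is one extra table from data already collected, and a less favourable bound printed beside the main result.
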